### **3. Clinical Laboratory Tests**

Blood samples will be collected for testing, including complete blood count (CBC), blood biochemistry, C-reactive protein (CRP), and erythrocyte sedimentation rate (ESR).

### **4. Histological Assessment**

Colon biopsies will be performed during colonoscopy for histological evaluation.

## **5. Assessment Schedule (Table 2)**

### **1. Screening and Group Assignment Visit (-21 Days to Day 0)**

For all consenting patients, baseline demographic and clinical information was collected prior to group assignment, including: Age, gender, and smoking status (current smoker, former smoker, or non-smoker).

- (1) Use of nonsteroidal anti-inflammatory drugs (NSAIDs) or other anticoagulants.
- (2) Use of proton pump inhibitors (PPIs), H2 receptor blockers (H2RB), or other antacids.
- (3) Presence of primary sclerosing cholangitis (PSC).
- (4) History of appendectomy.
- (5) Duration and severity of ulcerative colitis (UC).
- (6) Current treatments and medications.
- (7) Self-reported medication adherence.

Eligible participants were then randomly allocated in a 1:1 ratio to two parallel groups to receive FMT from either a Han donor or a Bai donor.

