### Exclusion Criteria:

- (1) Participants unable to provide informed consent, answer questionnaires, or supply samples.
- (2) Pregnant women or those attempting to conceive.
- (3) Participants unwilling to use effective contraception throughout the study.
- (4) Participants deemed in remission by investigators.
- (5) Evidence or history of toxic megacolon.
- (6) Isolated rectal inflammation (<5 cm in extent).
- (7) Diagnosed with Crohn's disease or indeterminate colitis.
- (8) Participants with perianal diseases (e.g., fistulae, anal fissures).
- (9) History of significant gastrointestinal surgery (e.g., colectomy) :
  - Minor surgeries will be reviewed case by case.
  - Patients with appendectomy within 3 months will be excluded.
- (10) Antibiotic use within the past 4 weeks for any reason, including for UC.
- (11) Steroid dependence requiring >20 mg prednisone or >9 mg budesonide daily at enrollment.
- (12) Recent or anticipated usage of prohibited drugs during the study period, including:
  - Rectal corticosteroids within 2 weeks prior to the first FMT.
  - Biologics (e.g., infliximab, adalimumab, vedolizumab) within 4 weeks prior to the first FMT.
  - Other major immunosuppressants (e.g., calcineurin inhibitors, antitumor drugs) within 12 weeks prior to treatment.
  - Probiotics within 4 weeks before the first FMT.
  - Experimental drugs or protocols within 12 weeks before the first FMT.
  - Anti-tuberculosis (TB or MAC) treatment within 4 weeks before the first FMT.

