#### Permitted Medications:

Participants may continue using the following medications if doses are stable within specified timeframes before the first FMT:

- Oral 5-aminosalicylic acid (stable for 4 weeks).
- Azathioprine and methotrexate ( $\geq 90$  days of use with stable doses for 4 weeks).
- Oral prednisone ( $\leq 20$  mg/day, stable for 2 weeks, gradually tapered at a rate of 2.5 mg/week to discontinue by week 8).

Subjects should maintain the same doses of oral 5-aminosalicylates, thiopurines, and methotrexate during the study. For oral prednisolone, the dose had to be tapered off gradually, at a rate of 2.5mg per week, so that subjects were no longer exposed to steroids until week 8.

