### **2. Treatment and Follow-Up (Week 0 to Week 12)**

Participants will undergo two colonoscopies with biopsies performed at two time points: before treatment, at 8 – 12 weeks post-FMT

Stool samples will be collected at the following times: before treatment, at the end of FMT treatment, 8 weeks post-FMT, 12 weeks post-FMT.

During each visit, Mayo scores (including endoscopic subscoring) were evaluated by blinded outcome assessors. Biopsies were performed for histological assessments, and histological scoring was conducted by a blind pathologist. A dedicated telephone line was available for patients to report any adverse events or worsening of symptoms between scheduled visits. All investigators were aware of group allocation, while endoscopists, pathologists, and outcome assessors remained fully blinded to group assignments to minimize assessment bias.

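### Group assignment may fall up to 21 days before the first FMT, while most washout and dose-stability windows end at it and no re-check is scheduled, leaving room for selective loss after randomisation

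*Combined protocol and SAP*

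**What the plan says.** **Timing of allocation.** Under 5. Assessment Schedule, the first visit is headed "Screening and Group Assignment Visit (-21 Days to Day 0". Baseline data come first; then "Eligible participants were then randomly allocated in a 1:1 ratio to two parallel groups". The day of allocation within the window is not fixed.

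**Anchors of the drug rules.** Exclusion criterion 12 counts most washouts back from the first infusion: "Rectal corticosteroids within 2 weeks prior to the first FMT", biologics "within 4 weeks prior to the first FMT", "Probiotics within 4 weeks before the first FMT" and "Experimental drugs or protocols within 12 weeks before the first FMT". Under Permitted Medications, concomitant drugs may continue "if doses are stable within specified timeframes before the first FMT": 2 weeks for prednisone, and 4 weeks for 5-aminosalicylic acid, azathioprine and methotrexate. Two rules use other anchors. The antibiotic exclusion looks back 4 weeks without naming FMT, and steroid dependence is judged at enrolment.

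**Checks.** The first table of the Sample collection plan marks the inclusion and exclusion criteria once, in the day -21 to 0 column. The infusions are in the week 1 column. The pregnancy test is repeated there; no medication check is.

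**Who knows the arm.** Under Treatment and Follow-Up, "All investigators were aware of group allocation", while endoscopists, pathologists and outcome assessors are blinded. The Blinding Maintenance section also says that investigators know the donor, but its next sentence restricts that knowledge to preparation staff.

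**Analysis set.** Section 11 builds the modified intention-to-treat set from participants with at least one infusion. No analysis of all randomised participants is planned.

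**The concern.** A patient's status can change between assignment and first infusion: a probiotic is started, a dose is altered, a rectal steroid is used. If this happens before allocation, the patient is an ordinary screen failure and the comparison is untouched. If it happens after allocation, there are two routes, and both act on a randomised patient.

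- **The patient is not infused.** The patient then drops out of the modified intention-to-treat set. Whoever decides to infuse, postpone or withdraw may know the donor group, and no planned analysis would show an imbalance.
- **The patient is infused despite the breach.** The handling is unclear. Section 11 counts protocol violators as failures. Prohibited Medications keeps users of prohibited drugs during the study enrolled and evaluated, without saying whether the gap before the first FMT counts as during the study.

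A gap is plausible in practice. The product is fresh and specific to the arm, so stool has to be arranged by donor group. That the delay might differ between arms is an inference from this; the protocol does not say so.

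**Working it through.** The point rests on no power or sample-size figure. Section 10 gives only 50 + 50 = 100, with no rates or power, so there is no derived figure to reproduce. The check is day arithmetic.

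**Inputs**

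- Gap from assignment to day 0: 0 to 21 days (5. Assessment Schedule).
- 14-day windows: rectal corticosteroids (Exclusion Criteria); stable prednisone (Permitted Medications).
- 28-day windows: biologics as given in the Exclusion Criteria, probiotics, anti-tuberculosis treatment; stable 5-aminosalicylic acid, azathioprine and methotrexate.
- 84-day windows: other major immunosuppressants and experimental drugs. The immunosuppressant rule counts back from treatment, which I read as the first FMT.
- 90-day window: minimum use of azathioprine or methotrexate.
- Assumption: day 0 is the day of the first FMT. Study Design puts FMT at baseline.

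**Formula.** Share of a look-back window that falls after assignment = min(gap, window) / window.

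| Gap (days) | 14-day window | 28-day window | 84-day window | 90-day window |
|---|---|---|---|---|
| 21 | 14/14 = 100% | 21/28 = 75% | 21/84 = 25% | 21/90 = 23% |
| 14 | 14/14 = 100% | 14/28 = 50% | 14/84 = 17% | 14/90 = 16% |
| 7 | 7/14 = 50% | 7/28 = 25% | 7/84 = 8% | 7/90 = 8% |
| 0 | 0% | 0% | 0% | 0% |

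Two notes on the inputs. Prohibited Medications gives biologics 12 weeks, not 4; on that figure the share at a 21-day gap is 21/84 = 25%. And if the week 1 column means that infusion can come after day 0, the gap can exceed 21 days: at 28 days, all of a 28-day window falls after assignment.

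These are shares of a calendar window, not of patients. The documents give no rate at which patients break a window.

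**Possible effect on the comparison (assumed inputs).** Take 50 per arm and a true success rate of 35% in both arms, so 0.35 × 50 = 17.5 expected successes per arm. Suppose that only patients who would not have responded are lost before the first infusion, and only in one arm. The rate in that arm's modified intention-to-treat set is 17.5 / (50 − e), where e is the number lost:

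| Lost (e) | Rate in that arm | Spurious difference |
|---|---|---|
| 1 | 17.5/49 = 35.7% | 0.7 points |
| 2 | 17.5/48 = 36.5% | 1.5 points |
| 3 | 17.5/47 = 37.2% | 2.2 points |
| 5 | 17.5/45 = 38.9% | 3.9 points |

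This is the least favourable pattern for each number lost. Losses unrelated to outcome and arm would cost precision but create no such difference.

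**The case against.** Several stronger readings are tempting, and the documents do not support them.

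- **That eligibility cannot be known at randomisation.** This holds only when assignment precedes the first FMT. Assignment on day 0 is allowed and leaves nothing unverified. Criterion 12 also covers anticipated use, which can be judged beforehand, and the antibiotic and steroid-dependence rules can be assessed at assignment.
- **That unblinded staff must re-judge eligibility.** No re-check of any kind is described. If a randomised patient counts as on study, the written rule for prohibited drugs is retention with the use recorded, not an open choice to drop the patient.
- **That the qualifying Mayo score may be three weeks old.** This is one reading only. The first table of the Sample collection plan allows the score anywhere from day -21 to 0, but the second dates the pre-treatment biopsies to day 0, and only one colonoscopy before treatment is planned. The qualifying endoscopy may well fall on or near day 0.
- **That bias will follow.** Participants are blinded and both arms receive FMT, so patients' own breaches have no evident reason to differ by arm. Only selective action by staff would bias the result, and the documents describe none.

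These objections limit the point but do not remove it. A forecast of drug use is not verification, day 0 assignment is permitted but not required, and the single eligibility check, investigator knowledge of the arm and infused-only analysis set are all in the text.

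**Conclusion.** The point holds as a design weakness that is cheap to remove. As written, the plan permits allocation up to 21 days before the first FMT, with up to 100% of the 2-week windows and 75% of the 4-week windows still open. It does not say whether or by whom eligibility is then re-confirmed, and it would not show a selective loss in that interval. The documents do not show that such a loss will occur.

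The window shares assume that day 0 is the first FMT. The 0.7 to 3.9 point illustration assumes 35% success, 50 per arm, and 1 to 5 losses confined to non-responders in one arm. With no breach rate given, the number of patients affected cannot be estimated. This merits a change to the schedule, but it is not a fatal flaw.

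**What to change.** 1. Keep screening from day -21, but separate it from allocation. Release the randomisation code only after washouts, stable doses and current symptoms are re-confirmed on a short checklist, on the day of the first FMT or within about 48 hours before it.
2. If fresh-stool logistics prevent this, have existing staff who are unaware of the arm do the re-check. The blinded outcome assessors are an obvious choice.
3. Report all randomised participants by arm, with reasons for any non-infusion.
4. The sponsor must reconcile the differing time anchors in the Exclusion Criteria, Permitted Medications and Prohibited Medications, and the two biologic washouts (4 and 12 weeks). The two statements in Blinding Maintenance on who knows the donor also need reconciling. Which clinical rule should apply is for the sponsor to settle; the point above does not depend on it.

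The cost is schedule wording, a checklist and one reporting table. The real downside is shorter notice for arranging fresh stool from a donor of the assigned group, so a donor from each group must be available around each first infusion. Donors of both groups are needed throughout enrolment in any case.

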### **2. Treatment and Follow-Up (Week 0 to Week 12)**

Participants will undergo two colonoscopies with biopsies performed at two time points: before treatment, at 8 – 12 weeks post-FMT

Stool samples will be collected at the following times: before treatment, at the end of FMT treatment, 8 weeks post-FMT, 12 weeks post-FMT.

During each visit, Mayo scores (including endoscopic subscoring) were evaluated by blinded outcome assessors. Biopsies were performed for histological assessments, and histological scoring was conducted by a blind pathologist. A dedicated telephone line was available for patients to report any adverse events or worsening of symptoms between scheduled visits. All investigators were aware of group allocation, while endoscopists, pathologists, and outcome assessors remained fully blinded to group assignments to minimize assessment bias.

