### **3. Results:**

1.Primary Outcome: The primary outcome is a composite of steroid-free clinical remission

together with endoscopic remission or response at week 12, defined as a total Mayo score of  $\leq 2$  points with no individual sub-score  $>1$  point, and at least a 1 point reduction from baseline in the endoscopy sub-score (MES).

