## 4. Methods:

**1. Study Design:** This is a patient single-blind, single-center, randomized, parallel-group pilot clinical trial without placebo control. Patients will be randomized to either the Han donor or the Bai donor and followed up for a 12-week period. Subjects will undergo follow-up assessments for up to 12 weeks in accordance with the same schedule as the blinded phase (i.e., FMT administration at baseline, weekly telephone follow-up at week 1, 8, and on-site follow-up visits at week 12). Subjects who are randomized to the FMT arm or who do not wish to enter the open-label phase will be deemed to have completed the study, and no further follow-up will be arranged.

Note: Single-center means all experimental activities are conducted at the same location.

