## Sample collection plan

Study visit (day/week)	Screening & Vist (Day)	Treatment & Follow &Up (Week)	Treatment & Follow &Up (Week)	Treatment & Follow &Up (Week)
	-21 to 0	1	8	12
Window period (day)	0	0		
Informed consent	x			
Inclusion and exclusion criteria	x			
Demographics and medical history	x			
Pregnancy test (if applicable)	x	x		
Infusion of FMT		Xxx (The Bacterial solution was given at an interval of one day, and a total of 100 mL was transplanted 3 times)		
Mayo score (including MES)	x		x	
Clinical laboratory test	x	x	x	
Fecal calprotectin	x	x	x	x
Adverse.events/serious adverse events		x	x	x

Follow-up Time Points

Groups  (40 Patients/Group)	Samples	Before FMT ( Day )	Follow Up ( Week )	Follow Up ( Week )	Follow Up ( Week )
		Baseline (0)	1	8	12
Fresh fecal bacterial solution  (Normal /Ethnic Han Donor)	Stool	✓	✓	✓	✓
	Biopsies	✓			✓
	Food Record Questionnaire	✓	✓	✓	✓
Fresh fecal bacterial solution  ( Bai Ethnic Donor)	Stool	✓	✓	✓	✓
	Biopsies	✓			✓
	Food Record Questionnaire	✓	✓	✓	✓

Note: (The procedures of sample collections and subpackaging are as follows)

- ① Study stool: The stool of patients are collected and packed into 2ml cryogenic vials.
- ② Study biopsies: One piece was selected from the ileocecal region and two pieces were taken from the most severe lesion of the rectum (10cm from the anus) and placed in a 2ml cryopreserved tube.

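### The primary endpoint is set at week 12, but its only follow-up colonoscopy may be done from week 8, so it can be scored up to four weeks early

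*Combined protocol and SAP*

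**What the plan says.** All references are to the combined protocol and SAP.

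- **Endpoint** (3. Results, 1. Primary Outcome): a steroid-free composite, "together with endoscopic remission or response at week 12". It needs a total Mayo score of 2 or less with no sub-score above 1, and a drop of at least one point from baseline in the endoscopic sub-score (MES).
- **Colonoscopies** (5. Assessment Schedule, 2. Treatment and Follow-Up): two per participant, "performed at two time points: before treatment, at 8 – 12 weeks post-FMT". The same section also has the Mayo score, endoscopic part included, assessed at every visit.
- **Visit table** (Sample collection plan): the row beginning "Mayo score (including MES" is marked at screening and, as the table reads after PDF extraction, at week 8. Week 12 is blank, and so are the window cells for weeks 8 and 12.
- **Sample table** (same section): biopsies are ticked at baseline and week 12. Under 4. Histological Assessment, biopsies are taken at colonoscopy.
- **Type of contact** (4. Methods, 1. Study Design): "weekly telephone follow-up at week 1, 8, and on-site follow-up visits at week 12".
- **Steroids** (Permitted Medications): oral prednisone up to 20 mg/day at entry, "gradually tapered at a rate of 2.5 mg/week to discontinue by week 8". In 11. Statistical Analysis, the treatment-failure rule uses week 12 as the date by which steroids must have stopped.
- **Blinding**: Treatment and Follow-Up keeps endoscopists, pathologists and outcome assessors blinded. It and 7.2 Blinding Maintenance say that investigators know the allocation.

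**The concern.** The component that decides the endpoint comes from one procedure, and that procedure has a date range whose earliest point is well before the time at which the endpoint is defined. Three things are at stake.

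1. **What is being estimated.** If some participants are scoped at week 8 and others at week 12, the remission proportion describes no single time point.
2. **How an early endoscopy enters the analysis.** It could be accepted as the week-12 result, treated as missing and dropped under the complete-case rule, or treated as a failure. The Statistical Analysis section does not choose, so the choice could be made after data are seen.
3. **Who sets the date.** Blinded readers protect the score. Nothing protects the choice of day within a four-week range from staff who know the donor group.

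The endpoint is also steroid-free. For participants who enter on the highest permitted prednisone dose, the early end of the range coincides with the end of the taper.

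**Working it through.** **Step 1. Reproduce the plan's own figure.** Inputs from Permitted Medications: highest entry dose 20 mg/day, taper 2.5 mg per week. Weeks to zero = dose / rate = 20 / 2.5 = 8, which agrees with the stated stop by week 8.

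**Step 2. Size of the timing gap.** Inputs: endpoint at week 12 (Primary Outcome); earliest permitted colonoscopy at week 8 (Treatment and Follow-Up). Gap = 12 − 8 = 4 weeks = 28 days, and 4 / 12 = 33% of follow-up. Weeks after FMT and study weeks are taken as the same clock.

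**Step 3. Steroid-free time at scoring.** The plan does not say when the first dose cut falls, so both cases are shown, with the taper assumed to begin with the first FMT. If the first cut is at the end of week 1, zero is reached at week dose/2.5. If it is on day 0, zero is reached one week earlier. Steroid-free weeks = scoring week − week of zero.

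| Entry dose (mg/day) | Reaches zero (week) | Steroid-free weeks at week 8 | Steroid-free weeks at week 12 |
|---|---|---|---|
| 20 | 7–8 | 0–1 | 4–5 |
| 15 | 5–6 | 2–3 | 6–7 |
| 10 | 3–4 | 4–5 | 8–9 |
| 5 | 1–2 | 6–7 | 10–11 |
| none | not applicable | unaffected | unaffected |

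**Step 4. Which week does the plan intend?**

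| Place | Week implied for the follow-up Mayo/MES |
|---|---|
| Primary Outcome | 12 |
| Treatment and Follow-Up, colonoscopy sentence | any from 8 to 12 |
| Treatment and Follow-Up, Mayo sentence | every visit, which two colonoscopies cannot supply |
| Visit table, Mayo row (as extracted) | 8 |
| Sample table, biopsies | 12 |
| Study Design | 12, because week 8 is a telephone contact and cannot yield an MES |

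The conflict between the first two rows is in plain prose and does not depend on either table.

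**Step 5. The two steroid dates.** Permitted Medications ends the taper by week 8; the failure rule looks at week 12. A participant whose taper ran late could be scoped at week 8 while still on steroids and stop before week 12. The steroid clause of the failure rule would not catch this. The separate clause on protocol violations might, but the plan does not say whether a late taper is such a violation.

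**Step 6. What cannot be computed.** The documents give no remission rates at week 8 or week 12 and no distribution of entry steroid doses. The size and direction of any effect on the Han–Bai difference are therefore unknown.

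**The case against.** The strongest reply is that this is a drafting slip and the intended week is clear. Study Design puts the only on-site follow-up visit at week 12, the follow-up biopsies are ticked at week 12, and the per-protocol set requires completion of 12 weeks. The same colonoscopy range applies to both randomised arms, and those who read the endoscopies are blinded. All of this stands. It shows which way to resolve the conflict, but it does not remove the sentence that permits week 8, and no rule covers what happens when that sentence is followed.

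Three further objections also stand and limit the point.

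- **The visit table is weak evidence.** A reader might infer from it that nobody has a week-12 endoscopic score. The single mark could be a cell merged across weeks 8 and 12, or a shifted one. The prose supports only that some participants may lack a week-12 score.
- **The plan sets no minimum steroid-free period.** A reader might infer that a week-8 score can never show steroid-free remission. The Primary Outcome does not require any duration off steroids, and the failure rule checks steroids by week 12 whatever the endoscopy date. The near-zero steroid-free time applies only near 20 mg/day.
- **Differential timing is a possibility, not a finding.** Nothing in the documents shows that dates would differ by donor group.

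One more reading is tempting. Study Design says that participants in the FMT arm, or those not entering an open-label phase, "will be deemed to have completed the study, and no further follow-up will be arranged". Since both arms receive FMT, this might seem to end follow-up for everyone. It comes after a 12-week schedule and reads naturally as nothing further after completion. With no open-label phase described, it looks like leftover text.

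**Conclusion.** The point holds as a contradiction within the plan about when the primary endpoint is measured. The endpoint is defined at week 12, while the only procedure that can supply its endoscopic part may be done up to 4 weeks earlier, and the analysis section has no rule for that case. The steroid aspect is real but confined to entrants at or near 20 mg/day: 0–1 steroid-free week at week 8 against 4–5 at week 12.

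The conclusion rests on the prose of the Primary Outcome and Treatment and Follow-Up sections. The steroid figures also assume that the taper starts with the first FMT and runs at the stated rate. No claim is made that the Han–Bai comparison is biased, or by how much. The point still needs correction before analysis, because it concerns the time point of the primary endpoint and leaves a choice that could be made once results are known.

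**What to change.** 1. **Treatment and Follow-Up:** replace the 8-to-12-week range with week 12 and a short stated window for the second colonoscopy and the full Mayo score with MES.
2. **Same section:** limit endoscopic sub-scoring to the two colonoscopies instead of every visit.
3. **Sample collection plan:** align the Mayo/MES row with week 12 and fill in the window cell. Nothing in this point requires the laboratory tests to move.
4. **Statistical Analysis:** state how a participant whose only follow-up endoscopy falls outside the window is counted in the primary analysis, and make that rule consistent with the failure and complete-case rules. A sensitivity analysis using every follow-up endoscopy whatever its date, and a table of days from first FMT to endoscopy by arm, would show whether timing differed.
5. **Steroids:** reconcile the week-8 date in Permitted Medications with the week-12 date in the failure rule. Which one applies is for the sponsor to decide.
6. **Study Design (secondary clean-up):** remove or explain the sentence about the FMT arm and the open-label phase.

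The cost is protocol wording, one row of the visit table and one analysis rule. The number of colonoscopies stays at two, and the second is tied to an on-site visit that already exists. What is given up is scheduling freedom between weeks 8 and 12.
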